4.3 Justification for dose

Doses of XXB750 and administration regimen were selected based on the safety, tolerability, and pharmacodynamic profile observed in preliminary data from the first-in-human trial of XXB750 (Study CXXB750A02101). This is an ongoing study investigating the safety, tolerability, and pharmacodynamics of single SC doses of XXB750 ranging from 1 mg to 600 mg. At the time of this protocol writing, XXB750 has been administered in healthy volunteers at doses of 1 mg, 3 mg, 10 mg, 30 mg, 60 mg, 120 mg, and 240 mg. There was no observed distinguishable effect on plasma cGMP or BP at doses of 1 mg, 3 mg, and 10 mg and placebo injection. XXB750 showed cGMP elevation and BP lowering effect at doses of 30 mg, 60 mg, 120 mg and 240 mg, which appeared to be greater than the effect of a placebo injection. For these doses, maximum plasma cGMP elevation was achieved at day 2 post-dose, and the BP lowering was slow and progressive, and achieved maximum effect by day 3. Placeboadjusted maximum office SBP lowering at day 3 was approximately 10-13 mmHg in the 30 mg, 60 mg, and 120 mg cohorts, and ~18 mmHg in the 240 mg cohort. The BPs showed a gradual return towards pre-dose values over the following weeks. At day 28 post-dose, plasma cGMP was lower than peak effect but still elevated at 30, 60, 120 and 240 mg dose compared to placebo, and the BP lowering effect was less pronounced than at peak, but still present in the 120 mg and 240 dose cohorts (SBP change from baseline of ~7 mmHg and ~5 mmHg, respectively). Given the sustained cGMP elevation and BP lowering and acceptable safety and tolerability profile, the 30 mg, the 60 mg, 120 mg, and 240 mg doses have been selected to be tested in this study to further investigate efficacy and safety of XXB750 in rHTN patients, and to support its use in subsequent studies as a once every 4 weeks SC administration regimen.

For more information about Study CXXB750A02101, please refer to the Investigator's Brochure.

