7.5 Early study termination by the Sponsor

The study can be terminated by Novartis at any time.

Reasons for early termination (may include, but are not limited to):

- Unexpected, significant, or unacceptable safety risk to participants enrolled in the study.
- Decision based on recommendations from applicable board(s) after review of safety and efficacy data.
- Discontinuation of study treatment development in rHTN.
- Changes in XXB750 development program that renders continuation of the study unnecessary.

In taking the decision to terminate, Novartis will always consider participant welfare and safety. Should early termination be necessary, participants must be seen as soon as possible and treated as a participant who discontinued from study treatment. Participants should be invited for EOT visit and Investigator should ensure the participant will be appropriately switched into Standard of Care therapy. The Investigator may be informed of additional procedures to be followed in order to ensure that adequate consideration is given to the protection of the participant's interests. The Investigator or Novartis (depending on local regulation) will be responsible for

informing IRBs (Institutional Review Board) /IECs (Independent Ethics Committee) of the early termination of the trial.

8 Study Assessments and Procedures

The Assessment Schedule (Table 1-2) lists all the assessments and when they are performed. All data obtained from these assessments must be supported in the participant's source documentation.

Participants should be seen for all visits/assessments as outlined in the assessment schedule (Table 1-2) or as close to the designated day/time as possible. Missed or rescheduled visits should not lead to automatic discontinuation.

Unscheduled visits can be performed by the site at the discretion of the investigator, in order to perform a safety evaluation or to retry assessments which were not completed at scheduled visits.

Visit 100 will be considered the reference visit for all study visits during the Randomized Treatment Period and Safety Follow-up Period. Regardless of the occurrence of any unscheduled visits, scheduled visits should be performed within the specified timeframe in relation to Visit 100 as outlined in Table 1-2. If a visit is completed earlier than scheduled or postponed, it should not result in the next visit being brought forward or postponed.

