The placebo run-in baseline is defined as the last available measurement prior to or at time of Visit 20. For some parameters, values may be only collected at screening (Visit 1) and then the placebo run-in baseline will be at screening for these parameters.

Unscheduled visit

Only for the analysis of safety evaluation (except ABPM and OBPM) will unscheduled measurements be taken into account. For ABPM, OBPM and efficacy evaluations, measurements from unscheduled visits will generally not be used, unless specified otherwise.

On-treatment data for an efficacy endpoint

In all the analyses planned in this document, on-treatment data refer to data collected while participants are on-study-medication or within 28 days after final study drug administration date for pre-mature permanent treatment discontinuation.

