Plasma glucose	> 25% increase
	value < 40 mg/dL
Blood pressure increase (mean mean mean mean mean mean mean mean	
Mean sitting office SBP (mmHg)	> 180 mmHg
Mean sitting office DBP (mmHg)	> 110 mmHg
Blood pressure decrease (mean m	neasurement)
1. Mean sitting office SBP (mmHg)	< 110 mmHg
2. Mean sitting office DBP (mmHg)	< 70 mmHg
3. Criteria 1 OR 2	Participants meeting either criterion 1 OR criterion 2
4. ABPM day time mean SBP (mmHg)	< 110 mmHg
5. ABPM day time mean DBP (mmHg)	< 70 mmHg
6. Criteria 4 OR 5	Participants meeting either criterion 4 OR criterion 5
7. ABPM night time mean SBP (mmHg)	< 90 mmHg
8. ABPM night time mean DBP (mmHg)	< 55 mmHg
9. Criteria 7 OR 8	Participants meeting either criterion 7 OR criterion 8
10. ABPM mean 24 hours SBP (mmHg)	< 105 mmHg
11. ABPM mean 24 hours DBP (mmHg)	< 65 mmHg
12. Criteria 10 OR 11	Participants meeting either criterion 10 OR criterion 11
13. Any one criteria	Participants meeting any one of the criteria 1 to 12
He aut mate't in anne :	
Heart rate* increase	. 400
Pulse (bpm)	> 100
Heart rate* decrease	
Pulse (bpm)	1. < 60
	0

2. < 50

Orthostatic hypotension

Parameter	Clinical notable criteria
Systolic blood pressure (mm Hg) minute after standing	≥ 20 mmHg reduction from corresponding mean measurement in sitting position
Diastolic blood pressure (mm Hg) minute after standing	≥ 10 mmHg reduction from corresponding mean measurement in sitting position
3. Systolic blood pressure (mm Hg) 3 minutes after standing	≥ 20 mmHg reduction from corresponding mean measurement in sitting position
4. Diastolic blood pressure (mm Hg) 3 minutes after standing	≥10 mmHg reduction from corresponding mean measurement in sitting position
5. Criteria 1 OR 2	Participants meeting either criterion 1 OR criterion 2
6. Criteria 3 OR 4	Participants meeting either criterion 3 OR criterion 4
7. Criteria 5 OR 6	Participants meeting either criterion 5 OR criterion 6
Liver function tests	
ALT (SGPT) OR AST (SGOT)	1. value > 3 x ULN
	2. value > 5 x ULN
	3. value > 8 x ULN
	4. value > 10 x ULN
	5. value > 20 x ULN
ALT (SGPT) OR AST (SGOT) AND	1. ALT or AST > 3 x ULN and TB > 1.5 x ULN
Total bilirubin (TB)	2. ALT or AST > 3 x ULN and TB > 2 x ULN
	3. ALT or AST > 5 x ULN and TB > 2 x ULN
	4. ALT or AST > 8 x ULN and TB > 2 x ULN
	5. ALT or AST > 10 x ULN and TB > 2 x ULN
	6. ALT or AST > 20 x ULN and TB > 2 x ULN
Alkaline phosphatase	1. > 2 x ULN
	2. > 3 x ULN
	3. > 5 x ULN
Total bilirubin	1. > 1.5 x ULN
	2. > 2 x ULN

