2.7.4.2 Vital signs

Vital signs including weight, blood pressure and pulse measures will be summarized by treatment group and scheduled visit with standard summary statistics (mean, Q1, median, Q3, standard deviation, min, max), including changes from randomization baseline. Graphical mean plots with 95% CIs for these vital signs will also be provided. Change from baseline will only be summarized for participants with both baseline and post-baseline values and will be calculated as:

[figure not shown]
• change from baseline = post-baseline value – baseline value

The number and percentage of participants with clinically notable vital signs after baseline will be presented in accordance with Table 2-4 for randomized treatment period and randomization period, by visit and overall. The analysis will be based on SAF.

Apart from the above analyses, values for vital signs parameters will also be listed at a participant level by treatment group and visit for all participants in safety set (SAF).

Maximum and minimum of 24 hour blood pressure and heart rate values will be summarized by visit (mean, Q1, median, Q3, standard deviation, min, max) for randomized treatment period and for randomization period.

[figure not shown]

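### SAP 2.1.1 keeps office BP from unscheduled visits out of safety analyses, so the overall low-BP and orthostatic counts in Table 2-4 could understate low BP found at unscheduled safety visits

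*SAP*

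**What the plan says.** SAP 2.1.1 sets the rule for unscheduled visits: "Only for the analysis of safety evaluation (except ABPM and OBPM) will unscheduled measurements be taken into account". The next sentence adds: "For ABPM, OBPM and efficacy evaluations, measurements from unscheduled visits will generally not be used, unless specified otherwise".

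SAP 2.7.4.2 then specifies a safety output: "The number and percentage of participants with clinically notable vital signs after baseline will be presented in accordance with Table 2-4". It is produced for the randomized treatment period and for the randomization period, by visit and overall, in the safety set.

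Table 2-4 (SAP 2.7.3) includes these BP criteria:
- Low office BP: mean sitting SBP below 110 mmHg or DBP below 70 mmHg.
- High office BP: mean sitting SBP above 180 mmHg or DBP above 110 mmHg.
- Orthostatic hypotension, at 1 or 3 minutes after standing: for systolic BP a "≥ 20 mmHg reduction from corresponding mean measurement in sitting position", and for diastolic BP a fall of at least 10 mmHg.
- Low 24-hour, daytime and night-time ABPM means.

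Protocol Section 8 gives the purpose of the extra visits: "Unscheduled visits can be performed by the site at the discretion of the investigator, in order to perform a safety evaluation". They may also be used to retry assessments missed at a scheduled visit. Protocol 9.4.2 plans the proportion of participants with notable vital signs and is silent on unscheduled readings.

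**The concern.** Hypotension is the risk the protocol expects from this drug, and Protocol 2.3 gives it as the reason for introducing the top dose in stages. A participant who feels unwell between visits may be brought in, and the office BP taken then is more likely than a routine reading to be low. Under SAP 2.1.1 a creatinine value from that visit counts toward Table 2-4, but the office BP from the same visit does not.

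At stake are the overall rows for low sitting BP and orthostatic falls. They are an objective complement to adverse-event reporting, because they do not depend on an investigator deciding that a reading is an adverse event. The same rule also removes unscheduled high readings.

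**Working it through.** The plan gives no figure to reproduce. The check is of the text and the visit schedule, followed by a scale calculation on stated assumptions.

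**Step 1: does anything restore the excluded readings?** SAP 2.1.1 excepts ABPM and OBPM from the use of unscheduled values in safety analyses. SAP 2.7, 2.7.3 and 2.7.4.2, as published, do not mention unscheduled BP. The visible rule therefore applies to the overall rows as well as the by-visit rows.

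**Step 2: could scheduled visits supply the same information?** In the first-in-human study "the BP lowering was slow and progressive, and achieved maximum effect by day 3". Injections are on Days 0, 28 and 56 (Protocol Table 1-2). The scheduled contacts that follow are:

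| Injection | Phone call | Next clinic visit | Days from injection to that visit |
|---|---|---|---|
| Day 0 | Day 3 | Day 14 | 14 − 0 = 14 |
| Day 28 | Day 31 | Day 56 | 56 − 28 = 28 |
| Day 56 | none | Days 59 to 63 | 3 to 7 |

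Only the third injection has a clinic visit within 7 days. In the top-dose arm the first 240 mg injection is on Day 28, and the next scheduled clinic visit is 28 days later. An office reading close to the peak of either of the first two injections would therefore come mainly from an unscheduled visit.

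**Step 3: direction within an arm.** The overall row counts participants who meet a criterion at any post-baseline time. Removing readings can lower that count or leave it unchanged; it cannot raise it.

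**Step 4: scale within an arm.** One participant in an arm of 34 is 100/34 = 2.9 percentage points. Let p be the share of an arm meeting a low-BP criterion when all readings are used, and q the share of those who meet it only on an unscheduled reading. Neither is in the documents. Assume p from 10% to 30% and q from 10% to 50%.
- Participants missed = 34 × p × q, from 34 × 0.10 × 0.10 = 0.3 to 34 × 0.30 × 0.50 = 5.1.
- Reported share = p × (1 − q). For p = 20% this runs from 18% (q = 10%) to 10% (q = 50%).

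**Step 5: difference between arms.** Take p = 30% in an active arm and 10% on placebo, a difference of 20 points.
- q = 25% in both arms: 22.5% against 7.5%, a difference of 15 points.
- q = 50% active, 10% placebo: 15% against 9%, a difference of 6 points.
- q = 10% active, 50% placebo: 27% against 5%, a difference of 22 points.

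The contrast between arms can shrink or grow, depending on a quantity that the documents do not give.

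**The case against.** The strongest reply is that the case of most concern, a symptomatic participant called in, is captured by another route. Symptomatic hypotension is an adverse event. SAP 2.7.1 counts adverse events by onset date, not by visit. SAP 2.7.1.1 gives hypotension its own query-based incidence, exposure-adjusted rate and time-to-first-event analysis, with serious hypotension and serious presyncope or syncope as events of special interest. This stands. A reader might infer that hypotension found between visits is lost from the safety analysis; it is not. The gap is confined to the measurement-based counts.

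A second reply is that a common visit schedule is a defensible basis for threshold counts. Arms with more unscheduled visits have more chances to cross a threshold, so including those readings makes ascertainment unequal. This stands as a reason to keep them out of by-visit summaries and to report their contribution separately. It is weaker for an any-time count, since the SAP already accepts unscheduled values for other safety measures such as laboratory tests.

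Third, the text is not complete. The second sentence of the rule is qualified, and SAP 2.1.1 refers to Section 2.12.1 for which OBPM measurements are eligible. That section is not in the public document, so an exception cannot be ruled out.

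Fourth, the 7-day window in the schedule check is a choice. Protocol 4.3 describes BP returning gradually over weeks, so the Day 14 visit still carries information. Week 9 also has a 24-hour ABPM after the third injection. This tempers the schedule argument but does not supply near-peak office readings after injections one and two.

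**Conclusion.** The point holds for the measurement-based counts. On the visible text, office BP from unscheduled visits is left out of the overall low-BP, high-BP and orthostatic rows of Table 2-4, and the low-BP and orthostatic rows could understate low BP as a result. The size is unknown: under the assumed ranges, about 0.3 to 5.1 participants per arm of 34.

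This rests on two inferences. OBPM is taken to mean office BP: it is not in the SAP abbreviation list, but Table 2-4 uses office-BP wording. Standing readings are taken to fall under it, supported by the standing office BP named in SAP 2.3.2. It also assumes that Section 2.12.1 contains no exception.

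Three stronger readings are tempting and not supported:
- That office BP alone is singled out. The rule excepts ABPM as well.
- That the relation between dose and low BP is biased toward no difference. Undercounting within an arm follows from the rule, but the effect on between-arm contrasts depends on how unscheduled-only cases are spread, as Step 5 shows.
- That the decision to open the 240 mg arm is affected. SAP 2.1 places DMC analyses under a separate plan, which is not available here.

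**What to change.** In SAP 2.1.1 and 2.7.4.2, state that post-baseline sitting and standing office BP from unscheduled visits enters the overall Table 2-4 rows for low BP, high BP and orthostatic hypotension, and is flagged in the participant listings. By-visit summaries and all efficacy analyses stay on scheduled visits. If Section 2.12.1 already provides for this, a cross-reference from both places is enough. Define OBPM in the abbreviation list at the same time.

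The cost is a short SAP statement and a small programming change. There are two drawbacks: the overall row will no longer equal the union of the by-visit rows, and arms with more unscheduled visits will have more chances to qualify. A footnote giving, by arm, the number of participants who qualify only on an unscheduled reading covers both and lets a reader recover the scheduled-only count.

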2.2 Analysis sets

The following analysis sets will be defined for statistical analysis:

Screened set (SCR) - All participants who signed the informed consent form. The SCR includes only unique screened participants, i.e., in the re-screened participants only the chronologically last screening data is counted.

D Somme

Run-in set (RIS) - All participants who have signed the informed consent and received at least one dose of single-blind run-in medication drug.

Randomized analysis set (RAS) - All randomized participants who received a randomization number, regardless of receiving trial medication.

Full analysis set (FAS) - All participants to whom study treatment has been assigned by randomization and who are not mis-randomized. Mis-randomized participants are those who have not been qualified for randomization, have been inadvertently randomized into the study and did not receive any double-blind study medication. According to the intent to treat principle, participants will be analyzed according to the treatment they have been assigned to during the randomization procedure.

Safety set (SAF) - All randomized participants who received at least one dose of double-blind study treatment. Participants will be analyzed according to the study treatment received, where treatment received is defined as the randomized/assigned treatment if the participant took at least one dose of that treatment or the first treatment received if the randomized/assigned treatment was never received.

Rules leading to exclusion from specific analysis sets of participants are provided in Appendix 5.5.

2.2.1 Subgroup of interest

Subgroups will be formed to explore the consistency of treatment effects and safety profiling on selected endpoints between the subgroups and the overall population.

In general, subgroups will be defined based on baseline information. In this study, since we have a run-in period to ensure that only participants whose BP remains elevated based on 24hr ABPM per the study entry criteria under study conditions while being treated with the run-in study medication (i.e. one injection of placebo matching XXB750) and optimal or maximally tolerated doses of triple background antihypertensive therapy (a thiazide/thiazide-like diuretic, an ACEI/ARB, and a long-acting dihydropyridine CCB) with good compliance before they can enter the randomized treatment period, we have defined baselines for different periods in Section 2.1. Subgroups will be formed using one of these baselines according to their analysis purposes.

Subgroups defined for selected endpoints in this study and the ways to derive them are listed in Table 2-1. The details about the subgroup analyses will be presented in the corresponding

sections as appropriate. Antihypertensive background medications taken at randomization will be listed by treatment group.

Table 2-1 Specification of subgroups

Subgroup Method of derivation		Background & Demographics / Exposure	Efficacy	Safety
Age groups: (<60 vs. ≥60 years)	Screening (derived)	X	Х	Χ
Age groups: (≤median vs. >median)	Screening (derived)	Х	Х	Х
Sex (male/female)	Screening	Х	Х	Х
Region*	Derived (pooled countries or country), using screening data	X	X	Х
eGFR (<60 vs. ≥60 mL/min/1.73m2)	Baseline		Х	Х
Number of background antihypertensive medications (=3 vs >3) **	Derived at randomization		Х	Х
Race (Asian and others, Black or African American, White)	Screening	X	Х	Х
Office SBP groups: (≤median vs. >median)	Baseline		Х	Х
History of diabetes (Yes, No)	Screening			Х
Weight (≤ median vs. > median)	Baseline		Х	X
	Derived			Х

^{*} America: USA

Asia: China, Taiwan, Japan

Eastern Europe: Bulgaria, Czechia, Poland, Slovakia

Western Europe and other: Austria, France, Germany, Italy, Spain, UK, Netherlands, Australia

^{**} If a participant takes both an ACEi medication and an ARB medication at randomization, it is counted as 2 for number of AHM.

2.3 Patient disposition, demographics and other baseline characteristics

2.3.1 Patient disposition

The number and percentage of participants screened successfully will be presented. In addition, screen failure participants will be summarized by primary reason for screen failure. For participants who are screened more than once, the information from the last screen will be used in the summary. The analysis is based on the screened set (SCR).

The number and percentage of participants enrolled and completed/failed in run-in will be summarized. The reasons for run-in failures will be provided. The analysis set is RIS.

The number and percentage of randomized participants (RAS) included in different analysis sets (Section 2.2) will be summarized by treatment group. The number and percentage as well as the reasons that participants had been excluded from RAS will be summarized by treatment. The number and percentage of randomized participants (RAS) and those in the full analysis set (FAS) who completed the study, who discontinued the study, and the reasons for discontinuation will be presented by treatment group, respectively.

In addition, the number and percentage of participants with protocol deviations (e.g. COVID related) as well as the criteria leading to exclusion from analysis sets will be provided for the participants in randomized set (RAS). Furthermore, the number and percentage of participants enrolled in run-in and randomized per region and per country will be presented for the RIS and the FAS, respectively. All disposition data will also be listed at participant level for randomization period disposition.

2.3.2 Demographics and other baseline characteristics

For the run-in period, summary statistics will be provided for the total number of participants pertaining to the Run-in set (RIS) for background and demographic characteristics, disease characteristics, and cardiovascular risk factors for the run-in period baseline. The following parameters will be included if applicable:

- Continuous variables: Age (in years), weight (in kilogram), height (in centimeter), body mass index (BMI, in kg/m²), sitting office systolic blood pressure (in mmHg), sitting office diastolic blood pressure (in mmHg), sitting pulse (in bpm), cyclic GMP (plasma and urine), cyclic GMP (urine)/urine creatinine, renin concentration, aldosterone, renin/aldosterone ratio, NT-proBNP, urine creatinine, eGFR and dose of antihypertensive background therapy of different classes.
- Categorical variables: Age group (<60 years vs. ≥60 years; ≤ median vs. > median), sex, race, ethnicity, region, number of background antihypertensive medications (=3 vs >3), history of diabetes (Yes, No), smoking history (Yes, No), current smokers (Yes, No), alcohol use history (0, >0 to 3, >3 drinks consumed per day in average), prior history of coronary heart disease (Yes, No), eGFR (<60 vs. ≥60 mL/min/1.73m2).

BMI will be calculated as weight (kg) / height² (m²) from the measured height and weight at Visit 1 (Screening Visit). Mean and SD of pack year will be summarized for current smokers and participants who have smoking history.

Similarly, for the randomized treatment period, summary statistics will be provided by randomized treatment group and overall for the above mentioned parameters in addition to: 24hr mean SBP (in mmHg), mean nighttime systolic blood pressure (in mmHg), mean daytime systolic blood pressure (in mmHg), 24hr mean DBP(in mmHg), mean nighttime DBP (in mmHg), mean daytime DBP (in mmHg),

standing office

systolic blood pressure (in mmHg), standing office diastolic blood pressure (in mmHg).

The summary will be presented for RIS and FAS, separately.

